### GROUP 2:

Each subject in Group 2 will participate in the study for up to 26 weeks, including up to approximately 3 weeks for screening, 22 weeks for treatment, and approximately 1 week for follow-up. SC injections of 128 mg CAM2038 q4w will be administered in the buttock, rotating between right and left buttock and injection site per Appendix 17.2, on Day 1, Day 29, Day 57 and Day 85, for a total of 4 doses. Following the first administration, subjects will attend an interim visit on Day 2 to evaluate safety and tolerability of the transition from SL BPN 24 mg to CAM2038 q4w.

Following administration of the first 3 doses, PK samples will be collected pre-dose and at scheduled times post-dose on an outpatient basis to determine achievement of steady state. To

Clinical Study Protocol Braeburn Pharmaceuticals HS-15-549 CONFIDENTIAL characterize steady state PK of BPN and norBPN, subjects will be confined to the CRU and serial PK samples will be collected for up to 24 hours following the fourth dose, administered on Day 85; subsequent PK samples will be collected up to 28 days post-dose on an outpatient basis. At the Day 113 (EOT) visit, CAM2038 q4w 128 mg subjects may continue on with open-label extension phase for up to 6 weeks and will be switched to CAM2038 q1w 32 mg, or transition back to standard care. For those subjects enrolling into the open-label extension, transition back to standard care will begin on Day 155 (EOT - OLE).

At each study visit, safety and efficacy assessments will be conducted at pre-specified times. Subjects will also be required to record their worst daily pain and average daily pain using an 11-point NRS on an electronic device.

#### GROUP 3:

Each subject in Group 3 will participate in the study for up to 21 weeks, including up to approximately 3 weeks for screening, 17 weeks for treatment, and approximately 1 week for follow-up. Single daily doses of 24 mg SL BPN will be administered in the mornings on Day 1 through Day 7 for a total of 7 doses. This will be followed by SC injections of 160 mg CAM2038 q4w in the buttock, rotating between right and left buttock and injection site per Appendix 17.2, on Day 8, Day 36, Day 64 and Day 92, for a total of 4 doses. Following the first CAM2038 q4w administration, subjects will attend an interim visit on Day 9 to evaluate safety and tolerability of the transition from SL BPN to CAM2038 q4w.

Following administration of the first 3 doses of CAM2038 q4w, PK samples will be collected pre-dose and at scheduled times post-dose on an outpatient basis to determine achievement of steady state. To characterize steady state PK of BPN and norBPN and evaluate relative bioavailability CAM2038 q4w as compared with SL BPN, subjects will be confined to the CRU and serial PK samples will be collected for up to 24 hours following the seventh dose of SL BPN administered on Day 7, and following the fourth dose of CAM2038 q4w administered on Day 92. Subsequent PK samples will be collected up to 28 days post-dose on an outpatient basis.

At each study visit, safety and efficacy assessments will be conducted at pre-specified times. Subjects will also be required to record their worst daily pain and average daily pain using an 11-point NRS on an electronic device.

For all Groups, subjects will be transitioned to standard care as needed at the EOT or EOT-OLE visit, as applicable, and a follow-up call will be conducted approximately 7 days after the last study visit. Subjects who discontinue early will undergo EOT visit assessments, including PK sampling and urine toxicology.

### **GENERAL CONSIDERATIONS:**

To ensure adequate enrollment and address potential inconvenience to subjects, all subjects will receive appropriate compensation for time and travel expenses related to attendance at study visits. All costs of medications will also be covered.

Section 10 provides additional information on the PK, efficacy and safety assessments included in the study. Statistical analyses are described in Section 12.

## 7.2 Discussion of Study Design

Subjects with current diagnosis of opioid use disorder (based on criteria defined in the Diagnostic and Statistical Manual of Mental Disorders – Fifth Edition [DSM-V]) or past medical history of opioid use disorder and currently being treated with SL BPN with concomitant chronic non-cancer pain will be enrolled in this study. Because this is the intended patient population, results from this study will be directly applicable to the therapeutic use of CAM2038 q1w and CAM2038 q4w in clinical practice. In addition to the requirement of opioid dependence, eligible subjects will be required to be on maintenance treatment of 24 mg SL BPN to ensure that the subjects will be able to safely tolerate the treatment dose levels planned for evaluation (32 mg CAM2038 q1w, 128 mg CAM2038 q4w, and 160 mg CAM2038 q4w).

As 1 of the 2 primary objectives, the study will evaluate the comparability of steady state exposure to BPN and norBPN after SC administration of CAM2038 q1w at different injection sites (Group 1) planned for treatment in a clinical setting, which will require rotation. Subjects allocated to Group 1 will first be administered CAM2038 q1w in the buttock, rotating between right and left buttock and injection site per Appendix 17.2, once weekly for the first 3 weeks to reach steady state. Once at steady state, CAM2038 q1w will be injected in the buttock (reference), abdomen, thigh and back of upper arm, using a randomized crossover design. A randomized crossover design will be used to minimize the variability in the study and avoid bias in the assignment of injection site sequence, as well as to increase the likelihood that known and unknown subject attributes (e.g., demographics and baseline characteristics) are evenly balanced across injection site sequence. Exposure to BPN and norBPN after administration of CAM2038 q1w will be evaluated by means of AUCss, Css,max, Css,av, time to Css,max (tss,max), norBPN/BPN ratios for Css,max and AUCss, and other derived PK parameters, as applicable.

The present study will also evaluate steady state PK of BPN and norBPN after 4 monthly injections of 2 dose levels of CAM2038 q4w in the buttock (128 mg [Group 2] and 160 mg [Group 3]). Steady state conditions will be confirmed by collecting pre-dose plasma samples prior to each SC administration for analysis of BPN and norBPN concentrations. Steady state exposure to BPN and norBPN will be characterized following administration of the last dose of CAM2038 q4w, with AUCss, Css,max, Css,av, tss,max, norBPN/BPN ratios for Css,max and AUCss and other PK parameters, as appropriate. Relative bioavailability of BPN will be assessed at steady state conditions after the fourth dose of 160 mg CAM2038 q4w and the seventh dose of 24 mg SL BPN (Group 3). Once the PK of 32 mg CAM2038 q1w and 128 mg CAM2038 q4w PK evaluation phases are over, subjects in Group 1 and Group 2 will have the option of receiving 6 more CAM2038 q1w 32 mg injections in an extension phase of the study.

In addition to evaluating the PK and safety of multiple doses of CAM2038 q1w and q4w, urine toxicology will be included as an exploratory efficacy measure of CAM2038 in maintaining opioid abstinence. Individuals who are in treatment for opioid dependence also commonly have a history of chronic pain (Rosenblum et al., 2003; Brands et al., 2004; Wiest et al., 2014). Long-acting transdermal BPN has proven effective in individuals with chronic cancer and non-cancer pain, with a reduction in the need for additional oral analgesics and improved quality of life (Likar et al. 2003; Sittl et al., 2005). Therefore, an additional exploratory objective of the current study is to assess daily pain intensity, as measured using an 11-point NRS, following SC administration of CAM2038 q1w and q4w.

# 8 SELECTION OF STUDY POPULATION

At least 20 subjects, but no more than 24 subjects, will be enrolled to Group 1 (CAM2038 q1w). Approximately 16 subjects will be enrolled into each of Group 2 (128 mg CAM2038 q4w) and Group 3 (160 mg CAM2038 q4w), for a total of approximately 32 subjects administered CAM2038 q4w. These sample sizes are consistent with typical PK studies. Replacement subjects may be added at the discretion of the Sponsor with the agreement of the Principal Investigator.

# 8.1 Inclusion Criteria

Subjects must meet each of the following inclusion criteria in order to be eligible for participation in the study:

- 1. Subject must provide written informed consent prior to the conduct of any study-related procedures.
- 2. Male or non-pregnant, non-lactating female subject, aged 19 to 65 years, inclusive.
- 3. Body mass index between 19 and 35 kg/m^2, inclusive.
- 4. Current diagnosis of moderate to severe opioid use disorder (according to the DSM-V) or past medical history of opioid use disorder currently being treated with SL BPN.
- 5. Subject must be taking SL BPN (Subutex® equivalent) 24 mg (Group 1 and Group 2) or ≥24 mg (Group 3) daily for at least 30 days prior to Screening.
- 6. Subject has a history of moderate to severe chronic non-cancer pain.
- 7. Male and female subjects of childbearing potential must be willing to use a reliable method of contraception during the entire study (Screening visit to Follow-up phone call) (Section 8.4.1).
- 8. Subject must be willing and able to comply with all study procedures and requirements.

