## 8.4 Study restrictions

In addition to the criteria described in Sections 8.1 and 8.2, the subject must agree to abide by the following study restrictions.

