## 8.4.1 Contraception Requirements

Male and female subjects of childbearing potential must be using and willing to continue using medically acceptable contraception during the study. Examples of medically acceptable forms of contraception include:

- True abstinence, defined as sexual inactivity consistent with the preferred and usual lifestyle of the subject. Note: Periodic abstinence (e.g., calendar, ovulation, symptothermal, post-ovulation methods) and withdrawal are not acceptable methods of contraception.
- Hormonal contraceptives (combined oral pill, patch or vaginal ring, intrauterine device or system, progestin implant or injection)
- Surgical sterilization (e.g. vasectomy or bilateral tubal ligation)
- Condom plus spermicidal agent (foam/gel/film/cream/suppository) during sexual intercourse with a female partner. In addition, the female partner should also be on another form of contraception (e.g., occlusive cap/diaphragm/intrauterine device/hormonal contraception, etc.) if she is of childbearing potential.
- To prevent exposure of any partner to the semen from a male subject who has been exposed to the investigational product, male subjects must use a condom during non-vaginal intercourse with any partner male or female.

The chosen contraception method(s) must be followed from the first administration of CAM2038 until at least 3 months after receiving the last dose of the investigational product.

Female subjects of non-childbearing potential are not required to use contraception or undergo pregnancy tests; however, they must be surgically sterile (hysterectomy and/or bilateral oophorectomy/salpingo-oophorectomy, as determined by subject medical history) or congenitally sterile, or must be post-menopausal. Post-menopausal is defined as being amenorrheic for at least 2 years without another cause or amenorrheic for at least 1 year without another cause and a documented follicle stimulating hormone (FSH) level ≥50 mIU/mL. If females are not amenorrheic for 2 years or amenorrheic for 1 year with a documented FSH level ≥50 mIU/mL or surgically sterile, then females will have to undergo the pregnancy procedures as stated in Table 1 (Group 1), Table 2 (Group 2), and Table 3 (Group 3).

Female subjects must not donate ova starting at Screening and throughout the clinical study period and for 3 months after final investigational product administration.

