# **10 STUDY PROCEDURES AND ASSESSMENTS**

All study assessments will be performed at the visits and the time points outlined in the Schedule of Assessments for Group 1 (Table 1), Group 2 (Table 2), and Group 3 (Table 3). The following sections outline the details and procedures associated with the assessments.
Study	Screening		Treatment Phase							Open-label Safety Extension Phase							
Treatment:				(	CAM2(	)38 q1w		CAM2038 q1w							FU		
CAM2038 q1w Dose:		I	Doses 1	to 3		Dos	es 4 to 7	Doses 8 to 13									
Day:	-21 to -1	D1	D2	D8	D15	D22, D29 D36, D43	D23-27, D30- 34, D37-41, D44-48	D50/ EOT	D57	D64	D71	D78	D85	D92/ EOT	D99/FU		
Informed Consent a	Х																
Eligibility Criteria Review b	Х	Х															
Medical, Psychosocial and Medication History	Х																
Substance Use and Treatment History	Х								1		1						
Complete Physical Examination	Х							X	1		1			Х			
Weight, BMI	Х							X						Х			
Height	Х																
Vital Signs C	Х	Х	X	X	Х	Х	Х	X	Х	X	X	X	X	X			
ECG d	Х	Х	X			Х	Х	X	X	X	X	X	X	X			
Biochemistry, Hematology, Urinalysis, and Coagulation Profile	Х	Х		Xe	X e	X e		X	X	X	X	X	X	X			
Pregnancy Test f	Х	Х		X	Х	X		X			X			Х			
Adverse Events g	Х	Х	Х	X	X	X	Х	X	X	X	X	Х	X	X	X		
Concomitant Medications/Procedures	Х	Х	Х	Х	Х	Х	X	Х	Х	Х	Х	Х	Х	Х	Х		

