#### Table 1: Schedule of Assessments – Group 1 (CAM2038 q1w) Campulation

a Subjects must voluntarily provide written informed consent prior to any study-related procedures being performed.

b Prior to treatment on Day 1, all Inclusion and none of the Exclusion criteria must be met.

c Vital signs (temperature, blood pressure, pulse rate, respiratory rate) will be measured pre-dose and 15 minutes' post-dose after each CAM2038 q1w administration and will be measured once at each non-dosing visit.

d ECG will be measured at the Screening and EOT visits, and pre-dose and 23 (±2) hours after the first CAM2038 q1w administration. ECGs will be measured at 1, 4, 6, 10, 24, 48, 72, 96 and 168 hours post-dose on doses 4 through 7.

e Assessment of serum sodium, bicarbonate, potassium, magnesium, calcium levels only.

 $^{\rm f}$  A serum pregnancy test will be performed at Screening and EOT visits. An "in-office" urine pregnancy test will be required prior to all doses of CAM2038 q1w (for women of childbearing potential) during days 1 through 50. An "in-office" urine pregnancy test will be required prior to all doses of CAM2038 q1w (for women of childbearing potential) for those women who continue in the extension phase will also be required.

g Any spontaneously reported AEs will be recorded after the subject signs the ICF. In addition, AEs will be elicited using a non-leading question each time the subject visits the clinic and once daily during inpatient stays.

Version: 5.0, 05 OCT 2016

Page 38 of 87

п5-15-549													 ΜΥΓΙ	DENT.	IAL
Study Period/Phase:	Screening			Tre	atment	Phase		Op	en-lab	el Sa	fety E	xtensi	on Pl	iase	
Treatment:				C	AM2038	8 q1w		CAM2038 q1w							FU
CAM2038 q1w Dose:			Doses	1 to 3		Da	oses 4 to 7	Doses 8 - 13							1
Day:	-21 to -1	D1	D2	D8	D15	D22, D29 D36,	D23-27, D30- 34, D37-41, D44-48	D50/ EOT	D57	D64	D71	D78	D85	D92/ EOT	D99 / FU
C-SSRS h	Х	Х	X	Х	Х	Х		X			X			X	
Injection Site Examination 		Х	X	Х	Х	Х	X	X	X	X	X	Х	X	X	
PK samples		X j		X j	Xj	Х	X k	X k						X	
cows 		Х	X	X	Х	Х		X						X	
sows 		Х	X	X	Х	Х		X						X	
UDS and Breath Alcohol Test	Х	Х	X	Х	Х	Х	X	X			X			X	
NRS for Pain m	Х	Х	X	Х	Х	Х	X	X	X	X	X	Х	X	X	
Randomization n		Х													
CAM2038 q1w SC injection 		X		X	Х	Х		X	X	X	X	X	X		

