	Total cholesterol (non-fasting)	

In addition to the clinical laboratory tests, a serum pregnancy test will be performed at the Screening and EOT visits. A urine pregnancy test will be required prior to all doses of CAM2038 q1w and q4w for all women of childbearing potential. Results must be reviewed and confirmed to be negative prior to start of CAM2038 treatment (Day 1).

The approximate total blood volume, including PK sample collections (Section 10.3.1.1) to be taken per subject during the study is the following:

- Group 1 total blood volume: approximately 546 mL
- Group 2 total blood volume: approximately 382.5 mL
- Group 3 total blood volume: approximately 352.5 mL

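### The contraception end point in inclusion 7 is shorter than the one in Section 8.4.1, and the pregnancy-test rows of Tables 1 and 2 mark only 2 of 6 extension doses although a test is required before every dose

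*Protocol*

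**What the plan says.** **Contraception.** Inclusion 7 in protocol Section 8.1 requires subjects of childbearing potential to be "willing to use a reliable method of contraception during the entire study (Screening visit to Follow-up phone call", and points to Section 8.4.1. The synopsis gives the same criterion and the same period without the pointer to Section 8.4.1. Section 8.4.1 says that the chosen method "must be followed from the first administration of CAM2038 until at least 3 months after receiving the last dose of the investigational product". Section 8.4 opens with: "In addition to the criteria described in Sections 8.1 and 8.2, the subject must agree to abide by the following study restrictions".

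**Pregnancy tests.** Footnote f of Table 1, attached to the pregnancy-test row, covers the extension explicitly: a "urine pregnancy test will be required prior to all doses of CAM2038 q1w (for women of childbearing potential) for those women who continue" into that phase. Footnote f of Table 2 has the equivalent rule. Section 10.5.3 repeats it for both products: "A urine pregnancy test will be required prior to all doses of CAM2038 q1w and q4w for all women of childbearing potential". In the extension columns, the row itself is marked on Days 50, 71 and 92 in Table 1 and on Days 113, 134 and 155 in Table 2. Days 92 and 155 are end-of-treatment visits without dosing.

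**The concern.** An eligibility check made on the wording of inclusion 7 alone looks for willingness up to the follow-up call, while another section of the same protocol sets a later end. A subject or site working from the synopsis would not be directed to the longer period. The call is also the last contact in each schedule, so nothing scheduled after it would prompt a question about contraception or pregnancy.

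For the tests, the grid is operative text. Section 10 runs all assessments at the visits and time points in the Schedules of Assessments, and Section 8.4.1 sends women who do not meet its definition of non-childbearing potential to Tables 1 to 3 for the pregnancy procedures. A site building visit worksheets from the marks alone would leave out most of the extension tests that the footnote requires. Section 10.5.2 makes further CAM2038 dosing depend on pregnancy status, so the test result has a direct use at those visits.

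**Working it through.** The plan states no figure for the interval from last dose to follow-up call, so there is none to reproduce. It follows from the schedules.

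**Step 1. Interval from last dose to call.** Dosing days come from Sections 7.1 and 9.1 and the injection rows of Tables 1 to 3. Call days come from the tables. For subjects who do not enter the extension, the call is taken as the end-of-treatment (EOT) visit plus about 7 days (Section 7.1). Interval = call day − last dose day. Shortfall = 3 months − interval, taking 3 months as 90 to 92 days (my assumption).

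| Path | Last dose | Call | Interval (days) | Shortfall (days) |
|---|---|---|---|---|
| Group 1, extension | D85 | D99 | 99 − 85 = 14 | 76 to 78 |
| Group 1, no extension | D43 | 50 + 7 = D57 | 57 − 43 = 14 | 76 to 78 |
| Group 2, extension | D148 | D162 | 162 − 148 = 14 | 76 to 78 |
| Group 2, no extension | D85 | 113 + 7 = D120 | 120 − 85 = 35 | 55 to 57 |
| Group 3, Table 3 (EOT D120) | D92 | D127 | 127 − 92 = 35 | 55 to 57 |
| Group 3, synopsis and SAP 4.3 (EOT D127) | D92 | 127 + 7 = D134 | 134 − 92 = 42 | 48 to 50 |

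The last two rows differ because the documents give two EOT days for Group 3. On either day the call comes well before 3 months.

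**Step 2. Injection row against pregnancy-test row, extension only.**

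| | Dosing days | Test marked | Test not marked |
|---|---|---|---|
| Group 1, Table 1 | D50, D57, D64, D71, D78, D85 | D50, D71 | D57, D64, D78, D85 |
| Group 2, Table 2 | D113, D120, D127, D134, D141, D148 | D113, D134 | D120, D127, D141, D148 |

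Unmarked: 4/6 = 67% of extension doses in each group, and 4 + 4 = 8 cells in all. In the main treatment phase every CAM2038 dosing day carries a test mark in all three tables. Group 3 has no extension.

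**Step 3. Could the blanks be lost in text extraction?** This is unlikely. In the same tables the vital-signs, ECG and laboratory rows are filled at every extension visit, while the C-SSRS and urine drug screen rows show the same sparse pattern as the pregnancy-test row. The row reads as a test every three weeks, which is not what its footnote says.

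**The case against.** The strongest reply is that neither pair of texts forces a breach. Section 8.4 is expressly additive, inclusion 7 in Section 8.1 points to 8.4.1, and inclusion 8 requires willingness to comply with all study requirements. A subject willing to use contraception only until the call therefore should not be enrolled. The 3-month period also recurs in the rules on ova donation, sperm donation and unprotected intercourse, so the sponsor's post-dose intention is not obscure. For the tests, footnote f hangs on the very row in question and Section 10.5.3 repeats it. An untested dose would mean overlooking both. All of this stands, and it makes the point one of inconsistent wording rather than a missing safeguard. It does not remove the inconsistency: inclusion 7 still names an explicit earlier end, the synopsis carries it without the pointer, and the grid still disagrees with its own footnote.

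A reader might infer more than the documents support:

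- **Screening, or the sublingual week in Group 3, is uncovered because 8.4.1 counts from the first CAM2038 dose.** It is covered. Section 8.4.1 opens by requiring contraception during the study, and inclusion 7 starts at Screening. For the same reason the Group 3 start needs no new anchor; its first CAM2038 dose is on Day 8.
- **Exclusion 6 is part of the contradiction.** It is limited to the study period and conflicts with no other text.
- **Section 10.5.2 has a reporting window that needs aligning.** It sets none; pregnancies are to be reported as soon as possible once known.

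The practical reach is also limited. Group 3 was added after randomization to Groups 1 and 2 was complete, so at this protocol version a change to inclusion 7 bears on eligibility mainly for the approximately 16 Group 3 subjects. The grid bears only on Group 1 and 2 subjects in the extension.

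**Conclusion.** The point holds as two internal inconsistencies in operative safety text. The end of contraception implied by inclusion 7 falls about 14 days after the last dose (Group 1, and Group 2 with the extension) or about 35 days after (Group 2 without the extension, and Group 3 per Table 3), against at least 3 months in Section 8.4.1. The Group 3 figure is about 42 days on the synopsis and SAP end-of-treatment day. With 3 months taken as 90 to 92 days, the shortfall is 48 to 78 days across all paths. The intervals are derived from the schedules, with the call about 7 days after the last visit; no section states them. The pregnancy-test rows omit 4 of 6 extension doses in each of Groups 1 and 2. The documents do not support saying that the protocol lacks the later contraception period or the tests. Both are required elsewhere in it, and the texts need to agree. Which contraception period or testing frequency is right is not judged here.

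**What to change.** Reconcile the end of the contraception period in inclusion 7, in both the synopsis and Section 8.1, with Section 8.4.1, so that all three places give the same end. Reconcile the pregnancy-test rows of Table 1 (D57, D64, D78, D85) and Table 2 (D120, D127, D141, D148) with footnote f and Section 10.5.3. The sponsor decides which text stands in each case. Any consent wording on contraception or testing should be checked against the result.

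The cost is amendment wording in two or three places, eight table cells or the matching footnote and 10.5.3 text, and a consent-form check. If the footnote stands, no procedure is added, because the tests are already required. The statistical analysis is unaffected.
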